**CONFIDENTIAL**

Date:  
Version:  
Status:  
Page:

30 November 2020  
5.0  
Final  
2 of 105

***Novo Nordisk***

## Protocol amendment summary of changes table

DOCUMENT HISTORY		
Document version	Date	Applicable in country(-ies) and/or site(s)
Protocol version 4.0	03 April 2020	China
Protocol version 3.0	01 July 2019	China
Protocol version 2.0	01 December 2017	China
Original protocol version 1.0	24 October 2017	China

### Overall rationale for preparing protocol, version 5.0

The overall primary rationale for updating the protocol was due to an error discovered in the Titration Guideline a1. In addition, minor updates to the protocol were implemented as outlined below.

Protocol  
Trial ID: NN1218-4357  
UTN: U1111-1197-8289

**CONFIDENTIAL**

Date: 30 November 2020  
Version: 5.0  
Status: Final  
Page: 3 of 105

**Novo Nordisk**

Section # and name	Description of change	Brief rationale
Section 2 Flowchart	Deleted X for 4 point profile at visit 2	The subjects will receive blood glucose meter at visit 2 and hence will not be able to perform 4 point profile prior to visit 2.
Section 2 Flowchart	Deleted X for Medication Error at V27 and P28	Medication Error should not be reported because the trial treatment has ended.
Section 2 Flowchart	Added footnote (f) for V10 ECG	Updated to align with timelines for ECG similar to visit 26.
Section 2 Flowchart	Deleted X for Drug Accountability at visit 9	Visit 9 this is not a dispensing visit and the subjects are not supposed to bring their trial product to the site at this visit, unless they do not continue in the trial.
Section 2 Flowchart	Footer description for footer f updated.	Text deleted to also cover visit 10 ECG.
Section 8.4.2 Hypoglycaemic episodes	Deleted text regarding reporting of hypoglycaemic episodes between visit 27 and phone visit 28.	Data on hypoglycaemic episodes between follow-up visit 1 (visit 27) and follow-up visit 2 (phone visit 28) is not collected since the subjects are using commercially obtained medication for which hypoglycaemic episodes should not be reported in the trial.
Section 8.4.4 Electrocardiogram (ECG)	Inserted visit 10	Updated to align with timelines for ECG similar to visit 26.
Section 8.5.2 Laboratory assessments for safety	Updated abbreviation of AST from Aspartate phosphatase to Aspartate aminotransferase.	Updated to be aligned throughout the protocol.

Protocol  
Trial ID: NN1218-4357  
UTN: U1111-1197-8289

**CONFIDENTIAL**

Date:  
Version:  
Status:  
Page:

30 November 2020  
5.0  
Final  
4 of 105

**Novo Nordisk**

Appendix A1: Insulin Titration Guideline for T1DM subjects, Table 3	
Updated table 3 as follows: Calculate the total daily dose of insulin. Adjust the basal-to-bolus ratio to be between 40:60 and 60:40. Use table 2 to find the total number of bolus insulin units and divide this value into three even or uneven doses of NovoRapid® to be taken with breakfast, lunch and dinner.
 
<del>Calculate the daily bolus units from the bolus component of the total daily dose. Divide the calculated number into three even or uneven doses of NovoRapid® to be taken with breakfast, lunch and dinner.</del>
	Updated to correct bolus insulin dose calculation.
---	---	--

**CONFIDENTIAL**

Date:  
Version:  
Status:  
Page:

30 November 2020  
5.0  
Final  
9 of 105

**CONFIDENTIAL**

Date:  
Version:  
Status:  
Page:

30 November 2020  
5.0  
Final  
10 of 105

## List of abbreviations

ADA	American Diabetes Association	IEC	independent ethics committee
AE	adverse event	IMP	investigational medicinal product
ALT	alanine aminotransferase	IRB	institutional review board
AST	aspartate aminotransferase	IWRS	interactive web response system
BG	blood glucose	LDL	low-density lipoprotein
CDS	Chinese Diabetes Society	LSFV	last subject first visit
CFDA	China Food and Drug administration	LSLV	last subject last visit
CRO	contract research organisation	NYHA	New York Heart Association
CTR	clinical trial report	OAD	oral antidiabetic drug
DUN	dispensing unit number	PCD	primary completion date
ECG	electrocardiogram	PG	plasma glucose
eCRF	electronic case report form	PPG	post prandial glucose
EASD	European Association for the Study of Diabetes	SAE	serious adverse event
EMA	European Medicines Agency	s.c.	subcutaneous(ly)
FAS	full analysis set	SD	Standard deviation
FDA	U.S. Food and Drug Administration	SmPC	summary of product characteristics
FPG	fasting plasma glucose	SMPG	self-measured plasma glucose
FSFV	first subject first visit	SUSAR	suspected unexpected serious adverse reaction
GCP	Good Clinical Practice	T1DM	Type 1 diabetes mellitus
HbA 1c	glycosylated haemoglobin	T2DM	Type 2 diabetes mellitus
hCG	human chorionic gonadotrophin	TEAE	treatment emergent adverse event
HDL	high-density lipoprotein	TMM	Trial Materials Manual
IB	Investigators Brochure	UTN	Universal Trial Number
ICH	International Conference on Harmonisation of Technical Requirements for Registration of Pharmaceuticals for Human Use		
ICMJE	International Committee of Medical Journal Editors		

Protocol  
Trial ID: NN1218-4357  
UTN: U1111-1197-8289

CONFIDENTIAL

Date:  
Version:  
Status:  
Page:

30 November 2020  
5.0  
Final  
12 of 105

Novo Nordisk

## 1 Summary

### Objectives and endpoints:

#### Primary objective:

To confirm the effect in terms of glycaemic control of treatment with fast-acting insulin aspart compared to NovoRapid® both in combination with insulin degludec with or without metformin in Chinese adults with type 1 diabetes mellitus (T1DM) or type 2 diabetes mellitus (T2DM) inadequately treated with a basal-bolus or a premix regimen, using a non-inferiority approach.

#### Secondary objective:

To compare the safety of fast-acting insulin aspart to NovoRapid® both in combination with insulin degludec with or without metformin in Chinese adults with T1DM or T2DM inadequately treated with a basal-bolus or a premix regimen.

#### Primary endpoint:

Change from baseline (week 0) in glycosylated haemoglobin (HbA1c) to 16 weeks after randomisation.

#### Secondary endpoints:

##### Supportive secondary efficacy endpoints:

- Change from baseline in 30- minutes, 1- hour, 2- hour and 3- hour post prandial glucose (PPG) increment to 16 weeks after randomisation (meal test)
- Change from baseline in 30- minutes, 1- hour, 2- hour and 3- hour PPG to 16 weeks after randomisation (meal test)
- Change from baseline in fasting plasma glucose (FPG) to 16 weeks after randomisation
- If a subject achieves HbA1c target 16 weeks after randomisation:
  - HbA1c < 7.0%
  - HbA1c < 7.0% without severe hypoglycaemia
- Change from baseline in 7-9-7-point self-measured plasma glucose (SMPG) to 16 weeks after randomisation:
  - Mean of the 7-9-7-point profile
  - 1-hour PPG and PPG increment (mean, breakfast, lunch, main evening meal)
  - Fluctuation in 7-9-7-point profile
- If a subject achieves PPG target (overall mean of daily PPG measurements in SMPG) 16 weeks after randomisation:
  - Overall PPG (1-hour)  $\leq$  7.8 mmol/L
  - Overall PPG (1-hour)  $\leq$  7.8 mmol/L without severe hypoglycaemia
- Insulin dose (Units/day and Units/kg/day; total basal, total bolus and individual meal insulin dose) 16 weeks after randomisation

Protocol  
Trial ID: NN1218-4357  
UTN: U1111-1197-8289

**CONFIDENTIAL**

Date:  
Version:  
Status:  
Page:

30 November 2020  
5.0  
Final  
13 of 105

**Novo Nordisk**

### **Supportive secondary safety endpoints:**

- Number of treatment emergent adverse events during the 16 weeks after randomisation
- Number of treatment emergent injection site reactions during the 16 weeks after randomisation
- Number of treatment emergent hypoglycaemic episodes classified both according to the American Diabetes Association (ADA) definition and Novo Nordisk definition during the 16 weeks after randomisation
  - Overall
  - Daytime and nocturnal hypoglycaemic episodes (00:01-05:59 – both inclusive)
  - Hypoglycaemic episodes from start of meal until 30 minutes, 1, 2, 4 hours and from 2 hours (exclusive) to 4 hours (inclusive) after start of meal

### **Trial design:**

This is a phase 3a, 16-week, multicentre, 1:1 randomised, double-blind, active controlled, treat-to-target, two-arm parallel group trial with an 8-week run-in period comparing the effect and safety of fast-acting insulin aspart to NovoRapid® both in combination with insulin degludec with or without metformin in subjects with T1DM or T2DM inadequately treated with a basal-bolus or a premix regimen. The trial includes two blinded dosing arms – mealtime fast-acting insulin aspart and mealtime NovoRapid®.

### **Trial population:**

A total of 505 subjects are planned to be screened and 300 subjects are planned to be randomised.

### **Key inclusion criteria:**

- Male or female, age above or equal to 18 years at the time of signing informed consent
- Diagnosed with T1DM  $\geq$  1 year prior to screening or diagnosed with T2DM  $\geq$  5 years prior to screening
- Treated with a basal-bolus insulin regimen or a premix insulin regimen  $\geq$  1 year prior to screening. Insulin regimen must be unchanged within 60 days prior to screening. A basal-bolus insulin regimen is defined as basal insulin once or twice daily and bolus insulin taken with meals at least thrice daily. A premix insulin regimen is defined as premix insulin twice or thrice daily
- For subjects with T1DM: not treated with any oral anti-diabetes drugs (OADs) for at least 90 days prior to screening  
For subjects with T2DM: not treated with any OADs or treated with 1-2 OADs within 90 days prior to screening. Allowed OADs are metformin, alpha-glucosidase inhibitor, SGLT2i and DPP4i. Change in OAD and dose prior to screening is allowed.
- HbA1c 7.5-9.5% (both inclusive) as assessed by central laboratory at screening

Protocol  
Trial ID: NN1218-4357  
UTN: U1111-1197-8289

**CONFIDENTIAL**

Date:  
Version:  
Status:  
Page:

30 November 2020  
5.0  
Final  
14 of 105

**Novo Nordisk****Key exclusion criteria:**

- Any of the following: myocardial infarction, stroke, hospitalisation for unstable angina pectoris or transient ischaemic attack within the past 180 days prior to the day of screening
- Subjects presently classified as being in New York Heart Association (NYHA) Class IV
- Planned coronary, carotid or peripheral artery revascularisation known on the day of screening
- Treatment with any medication for the indication of diabetes or obesity other than stated in the inclusion criteria within the past 90 days prior to the day of screening
- Anticipated initiation or change in concomitant medications (for more than 14 consecutive days) known to affect weight or glucose metabolism (e.g. treatment with orlistat, thyroid hormones, or corticosteroids)

**Randomisation criterion:**

- HbA1c ≤ 9.0% measured by the central laboratory at visit 9 (week -1)

**Assessments:**

- HbA1c
- PPG and PPG increment (meal test)
- PPG and PPG increment (7-9-7-point SMPG)
- Hypoglycaemic episodes
- Adverse events (AEs)

**Trial products:**

## Investigational medicinal products (IMPs):

- Test products:
  - Fast-acting insulin aspart, 100 U/mL solution for s.c. injection, 3 mL PDS290 pen-injector (blinded)
  - Insulin degludec (Tresiba®), 100 U/mL solution for s.c. injection, 3 mL PDS290 pen-injector
- Reference therapy:
  - Insulin aspart (NovoRapid®), 100 U/mL solution for s.c. injection, 3 mL PDS290 pen-injector (blinded)

## 2 Flowchart

Footer	Description
a	A 4-point SMPG profile should be performed on the three days prior to the visit/phone contact during the run-in and treatment period of the trial for titration purposes. The 4-point SMPG profiles can be part of the 7-9-7 point SMPG profile as appropriate.
b	The 7-9-7 point profiles should be measured on 3 consecutive days prior to the scheduled site visit.
c	SAEs only.
d	If an eye examination has been performed within the past 90 days prior to screening or in the period between screening and V2, and if the results are available at V2 then the procedure does not need to be repeated.
e	An eye examination must be performed at the randomisation visit (V10) or within 14 days prior to V10 (the results do not need to be available for randomisation).
f	ECG and eye examination obtained within 3 weeks prior to the visit is acceptable if the result is available at the visit.
g	ECG obtained less than 3 weeks prior to V1 as part of routine practice can replace the screening assessment if the results are available at V1.
h	Serum-HCG pregnancy testing should be performed on females with childbearing potential at visit indicated in the flowchart (analysed by central laboratory). If pregnancy is suspected between visits, a urine pregnancy test should be done locally. If test shows positive, then a confirmatory serum-HCG test should be sent to the central laboratory.
i	Start/stop date of trial product depending on when the subject discontinues/completes treatment.
j	Fasting is defined as at least 8 hours without drink or food intake (only water is allowed). If the subject attends the clinic in a non-fasting condition then the visit should be re-scheduled within the visit window. Diabetic medication should be withheld on the day of the visit until all blood samples have been taken.
k	On the last three days prior to visit/phone contact

Protocol  
Trial ID: NN1218-4357  
UTN: U1111-1197-8289

**CONFIDENTIAL**

Date:  
Version:  
Status:  
Page:

30 November 2020  
5.0  
Final  
21 of 105

**Novo Nordisk**

### 3 Background information and rationale for the trial

The trial will be conducted in compliance with this protocol, ICH GCP and applicable regulatory requirements, and in accordance with the Declaration of Helsinki.

In this document, the term investigator refers to the individual responsible for the overall conduct of the clinical trial at a trial site.

#### 3.1 Background information

Improvement in long-term glucose control, as obtained with intensified insulin therapy, may reduce the incidence of complications and delay the progression of existing complications in people with T1DM and T2DM. Postprandial hyperglycaemia contributes significantly to the HbA1c level and its control is thus essential for achieving the HbA1c target level. Postprandial hyperglycaemia is associated with increased risk of micro- and macro-vascular complications. Lowering of postprandial hyperglycaemia may reduce the progression of atherosclerosis and cardiovascular events in patients with T2DM.

Basal-bolus insulin therapy aims at mimicking the physiological insulin response in the healthy state to the largest possible extent. For that purpose, rapid-acting insulin analogues were developed to more effectively control the PPG excursions compared to subcutaneously injected human regular insulin, primarily through offering a faster onset and shorter duration of action. However, unmet needs exist within prandial insulin therapy for people with diabetes. The current insulin analogues are not able to match the speed of the normal physiological post meal insulin secretion, leading to suboptimal control of blood glucose, and an exogenous insulin with a faster glucose lowering effect is needed for tighter PPG control. In addition, a faster glucose lowering effect is also likely to offer greater flexibility in the time of dosing around meals thus increasing convenience for the patients and may allow the patients to better match the insulin taken to the meal.

For an assessment of benefits and risks of the trial, see Section [18.1](#).

##### 3.1.1 Therapeutic area

T1DM is a chronic disorder characterised by insulin deficiency and progressive complications due to hyperglycaemia. In T1DM a common treatment regimen is a basal-bolus therapy which was confirmed to be effective in reducing the incidence of late diabetic complications in the Diabetes Control and Complication Trial (DCCT). The ADA recommends an HbA1c target of less than 7.0% (<53 mmol/mol), without substantial hypoglycaemia.

Due to the progressive nature of T2DM, many patients are likely to be candidates for intensified insulin therapy. Prandial insulin supplementation is recommended by European Association for the Study of Diabetes (EASD)/ADA guidelines for treatment intensification in patients with T2DM who do not reach an HbA1c target below 7.0% on oral antidiabetic drugs (OADs) and basal insulin

Protocol  
Trial ID: NN1218-4357  
UTN: U1111-1197-8289

**CONFIDENTIAL**

Date:  
Version:  
Status:  
Page:

30 November 2020  
5.0  
Final  
22 of 105

**Novo Nordisk**

alone. The recommendation is a stepwise addition of bolus insulin when significant PPG excursions occur. A trial investigating step-wise addition of bolus insulin (basal-plus regimen) showed that around 75% of patients enrolled in the trial needed three boluses after 36 weeks of treatment in order to achieve an HbA1c below 7.0%. Results from the PREFER^11 trial indicated that one-third of the total prandial insulin dose is delivered with each meal in the majority of patients achieving HbA1c ≤7.0%. When used as part of a basal-bolus regimen in patients with T2DM who had previously received other insulin and/or OAD regimens, insulin aspart in combination with insulin degludec was a safe, well tolerated and effective treatment associated with clinically relevant reductions in hyperglycaemia.

### **3.1.2 NovoRapid® (Insulin aspart)**

Insulin aspart has been marketed in China since 2002, is marketed worldwide as NovoRapid® (US: NovoLog®) and is a rapid-acting insulin analogue indicated for the treatment of diabetes. In the remainder of this protocol, NovoRapid® will be applied as the trade name for insulin aspart in the marketed formulation.

NovoRapid® is homologous to human insulin, with the exception of the substitution of proline with aspartic acid at position B28. The rapid action of NovoRapid® is related to a weakened tendency of the insulin molecules to self-associate due to this modification and thereby is related to faster absorption as compared with regular human insulin. Compared with human insulin, NovoRapid® has a faster onset and a shorter duration of action, resulting in superior postmeal glucose control by means of lowering total glucose excursion following a meal, both in subjects with T1DM and in subjects with T2DM. This also allows NovoRapid® to be injected immediately before a meal, in contrast to regular human insulin which should be injected 30 minutes prior to the meal. For further details, please refer to the current version of the NovoRapid® local labelling.

### **3.1.3 Fast-acting insulin aspart**

Fast-acting insulin aspart (hereafter referred to as faster aspart, marketed as Fiasp®) is an innovative formulation of insulin aspart with two additional excipients which results in an increased early absorption of insulin aspart following subcutaneous injection. This leads to a greater early glucose-lowering effect compared to NovoRapid®. Faster aspart aims at approaching the physiological prandial insulin secretion pattern better than currently available treatment and thereby more effectively controlling the PPG excursions and achieving a better PPG control and increased flexibility in the time of dosing around meals compared with NovoRapid®. Results from clinical pharmacology trials in adults comparing pharmacokinetic and pharmacodynamic properties of faster aspart and NovoRapid® have shown that faster aspart resulted in an earlier onset of appearance and a greater early exposure to insulin aspart than NovoRapid® in subjects with T1DM, with the largest difference found within the first 15 minutes after injection. Faster aspart also

Protocol  
Trial ID: NN1218-4357  
UTN: U1111-1197-8289

**CONFIDENTIAL**

Date:  
Version:  
Status:  
Page:

30 November 2020  
5.0  
Final  
23 of 105

**Novo Nordisk**

resulted in a greater early glucose-lowering effect than NovoRapid®, but no statistically significant difference was found between faster aspart and NovoRapid® in total glucose-lowering effect.

In the global phase 3a programme, treatment with mealtime faster aspart effectively improved HbA1c in both subjects with T1DM and subjects with T2DM confirming non-inferiority between faster aspart and NovoRapid®. In a therapeutic confirmatory basal-bolus trial in adult subjects with T1DM, mealtime faster aspart in combination with insulin detemir effectively improved glycaemic control and the reduction in HbA1c was statistically significantly greater than with NovoRapid®. Mealtime faster aspart provided superior PPG control compared to NovoRapid® based on 2-hour PPG increment during a meal test. A statistically significant difference was also demonstrated for 1-hour PPG increment (meal test) in favour of mealtime faster aspart. No statistically significant difference was seen in overall rate of severe or blood glucose (BG) confirmed hypoglycaemic episodes between mealtime faster aspart and NovoRapid®. The rate during the first one hour after start of a meal, constituting a smaller fraction of all severe or BG confirmed hypoglycaemic episodes was statistically significantly higher for faster aspart compared to NovoRapid®. The overall safety profile for faster aspart and NovoRapid® was similar and as expected for insulin aspart.

In a therapeutic confirmatory basal-bolus trial in adult subjects with T2DM, adding and titrating mealtime faster aspart in combination with insulin glargine also effectively improved glycaemic control. Non-inferiority to NovoRapid® regarding HbA1c change from baseline was confirmed. A statistically significant benefit in 2-hour PPG increment (meal test) could not be confirmed for faster aspart compared to NovoRapid®. A statistically significant difference was demonstrated for 1-hour PPG increment (meal test) in favour of faster aspart compared to NovoRapid®. No statistically significant difference was seen in overall rate of severe or BG confirmed hypoglycaemic episodes between faster aspart and NovoRapid®. The rate during the first two hours after start of a meal, constituting a small fraction of all severe or BG confirmed hypoglycaemic episodes was statistically significantly higher for faster aspart compared to NovoRapid®. The overall safety profile for faster aspart and NovoRapid® was similar and as expected for insulin aspart.

Across the global phase 3a trials, faster aspart was well tolerated with similar safety profile as compared to NovoRapid®, with the most common adverse event being hypoglycaemia, similar to the levels observed with NovoRapid®. The insulin aspart molecule has a well-known safety profile based on more than 19 years of clinical experience. Compared to NovoRapid® faster aspart contains excipients which results in a faster initial absorption of insulin aspart following subcutaneous injection. The added excipients are included in the U.S. Food and Drug Administration's (FDA) list for approved drug products for injections, and no toxicological concerns have been predicted from subcutaneous use in humans at the proposed concentrations. For further details, please refer to the current edition of the Investigator's Brochure (IB) and any updates hereof.

Protocol  
Trial ID: NN1218-4357  
UTN: U1111-1197-8289

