#### 4.2.2 Secondary endpoints

##### 4.2.2.1 Supportive secondary efficacy endpoints

- Change from baseline in 30-minutes, 1-hour, 2-hour and 3-hour PPG increment to 16 weeks after randomisation (meal test)
- Change from baseline in 30-minutes, 1-hour, 2-hour and 3-hour PPG to 16 weeks after randomisation (meal test)
- Change from baseline in FPG to 16 weeks after randomisation
- If a subject achieves HbA1c target 16 weeks after randomisation:
  - HbA1c < 7.0%

Protocol  
Trial ID: NN1218-4357  
UTN: U1111-1197-8289

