## Additional analysis

Differences between the two populations will be investigated further by estimating the treatment differences separately for subjects with T1DM and T2DM. These treatment differences will be estimated based on the same data and a similar statistical model as the primary analysis but including interaction terms between treatment, stratification (T1DM and T2DM), and visit.

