### **Change from baseline in 30- minutes, 1- hour, 2- hour, and 3- hour PPG increment and 30- minutes, 1- hour, 2- hour, and 3- hour PPG to 16 weeks after randomisation (meal test)**

Laboratory measured PG from the meal test will be analysed for 30 minutes, 1-hour, 2-hours, and 3-hours PPG separately. The corresponding PPG increments will be derived separately using each PPG measurement minus the pre-prandial PG measurement.

Change from baseline in PPG and PPG increment endpoints 16 weeks after randomisation will be analysed based on the FAS using an ANOVA model including treatment and stratification (T1DM/T2DM) as factors, and with the corresponding baseline value as covariate.

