4.4 Secondary endpoints analyses

4.4.1 Supportive secondary endpoints

4.4.1.1 Efficacy endpoints

All endpoints except insulin dose in this section will be assessed using the FAS. Insulin dose will be presented using the safety analysis set.

Change from baseline in 30- minutes, 1- hour, 2- hour, and 3- hour PPG increment and 30-minutes, 1- hour, 2- hour, and 3- hour PPG to 16 weeks after randomisation (meal test)

Laboratory measured PG from the meal test will be analysed for 30 minutes, 1-hour, 2-hours, and 3-hours PPG separately. The corresponding PPG increments will be derived separately using each PPG measurement minus the pre-prandial PG measurement.

Change from baseline in PPG and PPG increment endpoints 16 weeks after randomisation will be analysed based on the FAS using an ANOVA model including treatment and stratification (T1DM/T2DM) as factors, and with the corresponding baseline value as covariate.

Change from baseline in FPG to 16 weeks after randomisation

Change from baseline in FPG to 16 weeks after randomisation will be analysed based on all planned post baseline measurements until or at 16 weeks after randomisation using a model similar to the primary analysis except with baseline FPG as covariate.

If a subject achieves HbA_{1c} target 16 weeks after randomisation

HbA_{1c} < 7.0%

A dichotomous (responder/non-responder) endpoint will be defined based on whether a subject has met the HbA_{1c} target (HbA_{1c} <7.0%) 16 weeks after randomisation.

This responder endpoint will be analysed based on a logistic regression model using treatment and stratification (T1DM/T2DM) as factors, and baseline HbA_{1c} as covariate. In the analysis, subjects who prematurely discontinue trial product and subjects with missing HbA_{1c} at 16 weeks will be included as non-responders.

HbA_{1c} < 7.0% without severe hypoglycaemia

A dichotomous (responder/non-responder) endpoint will be defined based on whether a subject has met the HbA_{1c} target (HbA_{1c} <7.0%) 16 weeks after randomisation without treatment emergent severe hypoglycaemic episodes.

This responder endpoint will be analysed based on a logistic regression model using treatment and stratification (T1DM/T2DM) as factors and baseline HbA_{1c} as covariate. In the analysis, subjects

who prematurely discontinue trial product and subjects with missing HbA_{1c} at 16 weeks will be included as non-responders.

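### Meal-test PPG has no planned estimate by diabetes type, although the 2-hour increment benefit was shown in a T1DM trial and not confirmed in a T2DM trial

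*Protocol*

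**What the plan says.** Protocol 3.1.3 summarises two earlier confirmatory trials of mealtime faster aspart.

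- In the T1DM trial: "Mealtime faster aspart provided superior PPG control compared to NovoRapid® based on 2-hour PPG increment during a meal test". For the earlier time point: "A statistically significant difference was also demonstrated for 1-hour PPG increment (meal test) in favour of mealtime faster aspart".
- In the T2DM trial, a statistically significant "benefit in 2-hour PPG increment (meal test) could not be confirmed for faster aspart compared to NovoRapid". For the earlier time point: "A statistically significant difference was demonstrated for 1-hour PPG increment (meal test) in favour of faster aspart compared to NovoRapid".

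The present trial enrols both types, with diabetes type as the randomisation stratum (protocol section 11). Meal-test PPG and PPG increment at 30 minutes and 1, 2 and 3 hours are supportive secondary endpoints (protocol 4.2.2.1). Protocol 17.4.1.1 analyses each one "using an ANOVA model including treatment and stratification (T1DM/T2DM) as factors, and with the corresponding baseline value as covariate". SAP 4.4.1.1 specifies the same model ("using an ANOVA model including treatment and stratification"), and SAP 4.5 declares no change from the protocol.

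Estimates by type do appear in the plan, but only under the primary HbA1c endpoint (protocol 17.3, SAP 4.3.3): "Differences between the two populations will be investigated further by estimating the treatment differences separately for subjects with T1DM and T2DM". That analysis uses a model with treatment, stratum and visit interactions.

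**The concern.** With diabetes type as a main effect only, the model assumes the same treatment difference in T1DM and T2DM and estimates that one number. If the true differences are unequal, the result is a weighted average that belongs to neither type, and no planned meal-test output would show this.

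The plan takes the by-type step for HbA1c, where section 3.1.3 reports non-inferiority in both types. It does not take it for the 2-hour PPG increment, where the same section reports results that came out differently.

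The meal test was included to compare postprandial regulation between the two insulins (protocol 5.2), and the results are meant to document efficacy in Chinese subjects with either type (protocol 3.2). A reader of the pooled figure could take a small value as no benefit in T1DM, or a favourable value as a benefit in both types. Neither could be checked without an unplanned subgroup analysis.

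**Working it through.** **Inputs from the documents.** Protocol 17.1: 270 evaluable subjects, 300 randomised, about 10% dropout, 20% T1DM assumed. Protocol section 7: T1DM at least 20% and T2DM at most 80%, controlled by the IWRS. Protocol section 11: 1:1 allocation, stratified by type. No PPG effect size, SD or power is given, so effects below are in SD units and are assumptions.

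**The plan's own figure.** HbA1c non-inferiority power with 135 per arm, SD 1.2, difference -0.02, margin 0.4, one-sided 2.5%:

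- SE = 1.2 × √(2/135) = 0.146; noncentrality = (0.4 + 0.02)/0.146 = 2.88.
- Noncentral t with 268 df gives 81.73%, against 81.7% stated.
- The other three table cells reproduce too (90.57%, 93.03% and 77.90%), and 270/(1 - 0.10) = 300.

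So 270 is a sound planning base for HbA1c, and I use it below.

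**Weights in the pooled difference.** With 1:1 allocation within each type, the additive model returns

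pooled = f × (T1DM difference) + (1 - f) × (T2DM difference),

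where f is the T1DM share. A least-squares fit to 54 T1DM and 216 T2DM subjects, with a T1DM effect of 1 and a T2DM effect of 0, returned 0.20. The baseline covariate is left out here.

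| T1DM share | T1DM weight | T2DM weight |
|---|---|---|
| 20% | 0.20 | 0.80 |
| 30% | 0.30 | 0.70 |
| 40% | 0.40 | 0.60 |
| 50% | 0.50 | 0.50 |

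**Precision of by-type estimates** (270 evaluable, 20% T1DM, equal variance in both types), in SD units:

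- Pooled: √(4/270) = 0.122
- T1DM: √(4/54) = 0.272, ratio to pooled √(270/54) = 2.24
- T2DM: √(4/216) = 0.136, ratio to pooled √(270/216) = 1.12
- Interaction: √(4/54 + 4/216) = 0.304

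**What each analysis could detect**, assuming an effect in T1DM only (two-sided 5%, normal approximation, opposite tail ignored):

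| Assumed T1DM effect | Pooled difference | Power, pooled | Power, T1DM estimate | Power, interaction |
|---|---|---|---|---|
| 0.3 SD | 0.06 SD | 7.1% | 19.6% | 16.5% |
| 0.5 SD | 0.10 SD | 12.7% | 45.1% | 37.6% |
| 0.8 SD | 0.16 SD | 25.9% | 83.6% | 74.8% |

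Under these assumptions the T1DM estimate shows a T1DM-only effect far better than the pooled one. It is still not a well-powered test unless the effect is large.

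**The case against.** The strongest reply is that the background is weak evidence of a difference between types. A reader might infer from section 3.1.3 that the earlier trials showed faster aspart to work on PPG in T1DM and not in T2DM. The documents do not support that. Significance in one trial and an unconfirmed benefit in another is not a demonstrated difference, and no estimates or intervals are given. The trials also differed in basal insulin (detemir against glargine), while the present trial uses degludec in both types. The 1-hour increment favoured faster aspart significantly in both. The contrast covers one of eight meal-test endpoints, with no by-type result for 30 minutes or 3 hours. All of this stands, and it confines the main case to the 2-hour increment.

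A reader might also infer that the pooled figure is in effect the T2DM result, or that opposite effects could cancel to zero. The first overstates an 80% share that is a ceiling. The second needs faster aspart to be worse in T2DM, by a quarter of the T1DM benefit at 20% T1DM (0.2 × 1 = 0.8 × 0.25). Nothing in the documents suggests this.

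It can further be said that these endpoints are supportive, that HbA1c already has by-type estimates, and that 54 T1DM subjects give little information. The meal test may also yield fewer than 270, since it requires a pre-meal glucose window (protocol 8.3.1) and is omitted after some treatment switches (protocol 8.1.9). These points are correct. They limit how the added estimates can be used, but they do not argue for leaving the estimates out.

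**Conclusion.** The point holds as a low-cost improvement to supportive analyses. It is not an error or a contradiction in the plan. The background gives a reason to view the 2-hour PPG increment by type, and the planned models cannot do so. At 20% T1DM a T1DM-only effect appears at 0.2 of its size, and at 30% to 50% T1DM at 0.3 to 0.5.

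The weights rest on 1:1 allocation within type. The standard-error ratios also assume equal variance in both types and a 20% share, and the absolute standard errors assume 270 evaluable subjects. The power figures rest on assumed effects of 0.3 to 0.8 SD. Whether the effect really differs by type is left open by the documents. The HbA1c conclusion and the sample size are untouched.

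**What to change.** In protocol 17.4.1.1 and SAP 4.4.1.1, keep the pooled ANOVAs as the main supportive analyses. Add that each model will also be fitted with a treatment-by-diabetes-type interaction, and that the T1DM and T2DM differences will be reported with 95% CIs. Name the 2-hour PPG increment as the main case and the other meal-test time points as descriptive. State that these are unadjusted estimates and not tests. Specify this before unblinding. If only the SAP is changed, record the addition in SAP 4.5.

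The cost is a sentence or two and one extra table from data already collected, using a by-type approach already planned for HbA1c. The downside is 16 further unadjusted intervals if all eight endpoints are shown (8 × 2). At 20% T1DM the T1DM intervals would be about 2.24 times as wide as the pooled ones. A wide T1DM interval that includes zero must not be read as absence of effect.
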